Objective(s):	The purpose of the study is to evaluate the efficacy of a dedicated MR-HIFU unit in ablating breast cancer with a non-invasive method. Primary objective: to evaluate the accuracy of MRI as a non-invasive method for assessment of treatment success. Secondary objective: Evaluation of treatment efficacy.
Outcome(s):	Primary endpoint: accuracy of MRI as method for assessment of qualitative and quantitative treatment success compared to the results of the histopathological analysis performed as reference method. Secondary endpoint: evaluate treatment efficacy (necrosis of tumor and safety margin >1mm)
Study design:	Single-center, single-arm, non-randomized trial

Inclusion / Exclusion criteria:	
Key inclusion criteria:
 
 - Biopsy proven ct1-2 N0-2 MX invasive breast cancer with a size of $\leq 3.0\text{cm}$. - Histological type of tumor: invasive ductal carcinoma (IDC) - Patient is scheduled for surgical resection of tumor at Kantonsspital Winterthur - Tumor location within the reach of the HIFU transducers with the patient in prone position; distance from skin and pectoral muscle to the tumor $\geq 1.0\text{ cm}$. - Target breast fits in the cup of the dedicated MR-HIFU breast system - 
Key exclusion criteria:
 
 - neoadjuvant systemic therapy - prior radiotherapy in target breast - contraindications for study procedures - macro-calcifications in or around the targeted tumor - scar tissue or surgical clips in the direct path of the ultrasound beams - Women who are pregnant or breast feeding,
--	--

	
Before treatment (Screening/Baseline):
 
 - Tumor assessment by MRI (routine procedure) - Location of tumor site - Check of inclusion/exclusion criteria - Medical history - Demographics, height, weight, WHO performance status - Baseline assessment of pain - Pregnancy test for women of child-bearing potential. 
Treatment (Study intervention):
 
Evaluations before MR-HIFU treatment:
 
 - Physical examination of breast - Assessment of pain - Assessment of adverse events - Assessment of changes in concomitant therapy 
Evaluations during MR-HIFU treatment:
 
 - DCE-MRI after treatment - Documentation of treatment parameters 
Evaluations before discharge of patient:
 
 - Physical examination of breast - Assessment of pain - Assessment of adverse events - Assessment of changes in concomitant therapy 
Follow-up (phone contact, day 2):
 
 - Assessment of pain. - Assessment of adverse events - Assessment of changes in concomitant therapy 
End of Study:
 
 - DCE-MRI - Physical examination of breast - Assessment of pain - Assessment of adverse events - Assessment of changes in concomitant therapy 
Surgery (non-study procedure): Surgical ablation of the tumor (histopathological analysis of tumor tissue).

--	--

Study Product / Intervention:	
Study product: Philips Sonalleve MR-HIFU Breast Therapy System
 
Study intervention: The breast tumor lesion of qualified study patients will be treated with MR-HIFU under procedural sedation. Two follow-up DCE-MRI scans will be performed for evaluation of treatment efficacy. The first DCE-MRI is done directly after the MR-HIFU treatment (patient still in sedation).
 
Treatment time:
 
 - MR-HIFU procedure including preparation and first DCE-MRI (2-3 hours) - Recovery time after procedure (ca. 3 hours). 
Follow-up MRI: The second DCE-MRI will be performed 8 (± 2) days after treatment (ambulant procedure).

Control Intervention (if applicable):	not applicable
Number of Participants with Rationale:	This project is performed as a proof-of-concept study with a limited sample of 10 patients.
Study Duration:	Estimated duration of main investigational plan: 13 month (patient recruitment: 12 month; duration of individual patient participation 2-3 weeks)
Study Schedule:	First-Participant-In (planned): Q1/2018 Last-Participant-Out (planned): Q2/2019
Investigator(s):	[name]. med. [name] Kantonsspital Winterthur Institut für Radiologie und Nuklearmedizin [name] Switzerland [contact] E-Mail: [contact]
Study Centre(s):	Single-center study

	
This proof-of-concept study will be analyzed predominantly with methods of descriptive statistics.
 
Primary outcome: Quantitative analysis: Comparison and correlation of results from histopathology and DCE-MRI regarding Size/Volume of tumor and volume/percentage of tumor necrosis
 
Qualitative analysis: Comparison of results from histopathology and DCE-MRI regarding spatial congruence of ablated tumor tissue and width of margin
 
Secondary outcome: Assessment of treatment efficacy (Effective treatment: complete necrosis of targeted tumor including safety margin (>1mm))
 
Safety analysis AEs in general and additional predefined safety parameters will be presented by type and grade in tables showing frequency.

Statement:	This study will be conducted in compliance with the investigation plan, the current version of the Declaration of Helsinki, the ISO EN 14155 as well as all national legal and regulatory requirements.

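### Is treatment efficacy scored on the very MRI scans whose accuracy the trial sets out to test?

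*Combined protocol and SAP*

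**What the plan says.** All references are to the synopsis of the combined protocol and SAP.

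- **Objective(s) row:** "Primary objective: to evaluate the accuracy of MRI as a non-invasive method for assessment of treatment success". Treatment efficacy is the secondary objective.
- **Outcome(s) row:** the primary endpoint sets MRI "compared to the results of the histopathological analysis performed as reference method". The secondary endpoint is efficacy, glossed as "necrosis of tumor and safety margin >1mm".
- **Study Product / Intervention row:** "Two follow-up DCE-MRI scans will be performed for evaluation of treatment efficacy". It then gives the timing: "The first DCE-MRI is done directly after the MR-HIFU treatment (patient still in sedation", with the second scan 8 ± 2 days after treatment.
- **Statistical analysis row:** histopathology and DCE-MRI are compared on tumour size, extent of necrosis, spatial agreement and margin width. The secondary outcome reads "Effective treatment: complete necrosis of targeted tumor including safety margin (>1mm").
- **Inclusion criteria and schedule:** "Patient is scheduled for surgical resection of tumor at Kantonsspital Winterthur" is an inclusion criterion. Surgery, though labelled as outside the study procedures, is listed as "Surgical ablation of the tumor (histopathological analysis of tumor tissue").

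The sample is ten patients in a single arm, and the analysis is mainly descriptive.

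**The concern.** Two things catch the eye. First, the sentence about the scans is the only one that attaches an assessment method to the term used for the secondary objective. Histopathology is called the reference only inside the primary endpoint. A literal reader could conclude that ablation success is to be judged on DCE-MRI, the method whose accuracy is still in question. Residual tumour that MRI missed would then be counted as a success, and a complete ablation that MRI misread would be counted as a failure.

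Second, the word for completeness appears in the statistical analysis row but not in the Outcome(s) row. Under the shorter wording, a partly necrotic tumour might be argued to qualify.

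Three readings per patient could be candidates: MRI directly after treatment, MRI at about day 8, and histology. With ten patients, each reclassified patient moves the success rate by 1/10, or 10 percentage points. If source and definition were truly open, the choice could be made after the results were known.

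**Working it through.** **Is there a figure to reproduce?** No. The plan gives no expected success rate, MRI accuracy, threshold or precision target, and the ten patients are justified only as a proof of concept. The check is therefore mainly one of reading, with arithmetic to show what would be at stake.

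**Step 1: which source does the plan supply for each part of the endpoint?** Efficacy has two components, necrosis of the tumour and a margin above 1 mm. The statistical analysis row requires histopathology to deliver extent of necrosis and margin width in order to compare them with MRI. The Outcome(s) row makes histopathology the reference for both qualitative and quantitative treatment success. Every patient who contributes to the primary comparison therefore has a reference reading of both components, and scoring efficacy on histology needs no further data.

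**Step 2: what does the sentence about the scans do?** It sits in the description of the intervention and explains why two scans are made. The primary objective gives MRI exactly the role of judging treatment success, to be checked against histology. The sentence is consistent with that role. It does not say that the secondary endpoint is read on MRI, on MRI alone, or in place of histology.

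**Step 3: do the two wordings conflict?** Both require a margin above 1 mm. Necrosis of the tumour together with a rim beyond it ordinarily means that the whole tumour is necrotic. The Outcome(s) row is a parenthetical short form, and the statistical analysis row gives the explicit definition.

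**Step 4: what if MRI were used anyway?** Let p be the true (histological) success rate, Se the probability that MRI calls success when histology does, and Sp the probability that MRI calls residual tumour when histology does. All three are assumptions.

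Apparent success = Se × p + (1 − Sp) × (1 − p)

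| p | Se | Sp | Apparent success | Shift (points) |
|---|---|---|---|---|
| 0.5 | 0.9 | 0.7 | 0.45 + 0.15 = 0.60 | +10 |
| 0.5 | 0.9 | 0.4 | 0.45 + 0.30 = 0.75 | +25 |
| 0.4 | 0.9 | 0.4 | 0.36 + 0.36 = 0.72 | +32 |
| 0.3 | 0.9 | 0.5 | 0.27 + 0.35 = 0.62 | +32 |
| 0.5 | 0.8 | 0.8 | 0.40 + 0.10 = 0.50 | 0 |
| 0.9 | 0.9 | 0.7 | 0.81 + 0.03 = 0.84 | −6 |
| 0.9 | 0.7 | 0.9 | 0.63 + 0.01 = 0.64 | −26 |

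The shift is zero whenever (1 − Sp)(1 − p) = (1 − Se)p, and it can take either sign. The documents do not allow its direction, let alone its size, to be stated.

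**Step 5: what if histology is used?** Then Se = Sp = 1 by construction and the shift is zero. Only sampling error remains. The exact (Clopper-Pearson) 95% intervals at n = 10 are 18.7% to 81.3% for 5/10, 34.8% to 93.3% for 7/10, 55.5% to 99.7% for 9/10, and 69.2% to 100% for 10/10.

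**The case for a change.** The strongest case for a change is that a reader should not have to choose between two readings. The only sentence that links a method to efficacy names MRI, and it uses the term of the secondary objective rather than that of the primary one. If MRI were used, the trial could not correct for its errors. Even if MRI detected every residual tumour, the exact lower 95% limit for Sp would be 2.5% with one such case, 29.2% with three and 47.8% with five. The repair would be a matter of wording only. Nor does a small sample excuse a biased estimate.

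Part of this stands. Neither statement of the secondary endpoint names its source, and the two wordings are not identical. It is also true that patients are only scheduled for resection, so histology is expected in all of them rather than guaranteed.

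The step from there to a flawed analysis does not stand. The bias depends on a choice that the plan nowhere makes and that its own structure argues against: an analyst holding the reference reading of necrosis and margin would have to set it aside in favour of the test being validated. A patient without resection would drop out of the primary comparison too, so missing tissue is not a weakness peculiar to this endpoint. Adding an exact interval or a treated-patient denominator may be good reporting practice, but neither corrects a wrong result on this point.

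**Conclusion.** No change is called for. The synopsis leaves the assessment source of a secondary, descriptive endpoint unnamed, and analysts would fill that gap sensibly with the reference method the trial already relies on. The difference in wording is a short form beside a full definition, with the same margin threshold.

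The stake is conditional: +32 to −26 points in the scenarios shown if MRI were the source, and no misclassification shift if histology is. No success threshold in the visible text turns on the result.

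This conclusion rests on three assumptions: that tissue from the planned resection is examined for necrosis and margin, as the primary comparison requires; that the definition in the statistical analysis row governs; and that the full investigation plan, of which only the synopsis is available here, does not state that efficacy is scored on MRI.

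### The primary endpoint is MRI accuracy, but correlation, the only statistic named for its quantitative analysis, cannot show whether MRI is accurate

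*Combined protocol and SAP*

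**What the plan says.** All references are to the synopsis in the combined protocol and SAP, which is the only text supplied.

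- **Outcome(s):** the primary endpoint is "accuracy of MRI as method for assessment of qualitative and quantitative treatment success compared to the results of the histopathological analysis performed as reference method".
- **Statistical analysis entry (unlabelled), Primary outcome, quantitative part:** "Comparison and correlation of results from histopathology and DCE-MRI regarding Size/Volume of tumor and volume/percentage of tumor necrosis". No coefficient is named. No mean difference, ratio, agreement measure or confidence interval is mentioned.
- **Same entry, qualitative part:** "Comparison of results from histopathology and DCE-MRI regarding spatial congruence of ablated tumor tissue and width of margin". No index is named here either.
- **Same entry, opening sentence:** "This proof-of-concept study will be analyzed predominantly with methods of descriptive statistics".
- **Study Product / Intervention:** "Two follow-up DCE-MRI scans will be performed for evaluation of treatment efficacy". On timing, "The first DCE-MRI is done directly after the MR-HIFU treatment", and the second scan follows at 8 (± 2) days. The screening list also includes a routine MRI tumour assessment before treatment. The analysis entry does not say which scan is set against histopathology for which quantity.
- **Number of Participants:** "This project is performed as a proof-of-concept study with a limited sample of 10 patients".

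**The concern.** Accuracy against a reference method asks how far the MRI value lies from the histopathology value. Correlation asks a different question: whether patients with larger histopathology values also have larger MRI values. MRI could overstate every volume by half and still correlate almost perfectly with histology.

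The word comparison may be meant to cover the difference between the two methods, but the synopsis does not say so. If the report led with the one statistic that is named, the quantitative half of the primary endpoint would be answered by a number that is blind to systematic error. What is at stake is how the primary result can be read. No data would be lost and no decision in the synopsis depends on the coefficient.

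**Working it through.** **Inputs from the documents.** n = 10; tumour size at most 3.0 cm; two post-treatment DCE-MRI scans. The synopsis gives no standard deviation, noise level, expected bias or precision target, and no calculation behind the ten patients, so there is no planned figure to reproduce.

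**Step 1: invariance (no assumptions needed).** For any constant a and any b > 0, corr(X, a + bY) = corr(X, Y). Ranks are also unchanged, so the same holds for Spearman. A constant shift or a constant factor in the MRI readings therefore leaves both coefficients where they were.

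**Step 2: a constructed example.** Take ten reference values 10, 20, …, 100 (mean 55, variance 825 with divisor 10).

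- MRI reads 30% low throughout: r = 1.00. The mean difference is −0.3 × 55 = −16.5. Lin's concordance is 2 × 0.7 × 825 / (825 + 0.49 × 825 + 16.5²) = 1155 / 1501.5 = 0.77.
- MRI reads 20 units low throughout: r = 1.00. The mean difference is −20. Concordance is 2 × 825 / (2 × 825 + 20²) = 1650 / 2050 = 0.80.

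**Step 3: with noise at n = 10 (assumed inputs).** 20,000 simulated studies; diameter d uniform on 1 to 3 cm; volume = (π/6)d³; MRI volume = bias factor × volume × lognormal noise. The interval is the paired t-interval on log(MRI/histopathology), back-transformed to a ratio.

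| Noise | True MRI/histology ratio | Median Pearson r | Median Spearman | Studies whose ratio CI excludes 1.0 |
|---|---|---|---|---|
| 10% | 1.0 | 0.99 | 0.99 | 5% |
| 10% | 1.3 | 0.99 | 0.99 | 100% |
| 10% | 1.5 | 0.99 | 0.99 | 100% |
| 20% | 1.0 | 0.97 | 0.95 | 5% |
| 20% | 1.3 | 0.97 | 0.95 | 96% |
| 20% | 1.5 | 0.97 | 0.95 | 100% |

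For the 30% over-read, a typical 95% CI for the ratio is 1.21 to 1.39 at 10% noise and 1.13 to 1.49 at 20% noise. For tumour size with an assumed constant error of +3 mm and 2 mm noise, r stays at 0.95 with or without the error. The paired-difference CI is typically 1.6 to 4.4 mm and excludes 0 in 99% of studies.

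The choice of coefficient matters. An absolute-agreement intraclass correlation does respond to bias: at 10% noise it is 0.99, 0.90 and 0.80 for ratios of 1.0, 1.3 and 1.5.

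**Step 4: precision of the alternative.** The 95% CI half-width for a mean paired difference at n = 10 is t(0.975, 9)/√10 = 2.262/3.162 = 0.72 SD of the paired differences. The documents give no SD, so this cannot be turned into millimetres, millilitres or percentage points.

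**The case against.** The strongest reply has four parts.

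1. **This is a synopsis.** It refers to an investigation plan and to predefined safety parameters that are not in the supplied text, so the measure and the scan pairing may be specified elsewhere. This stands, and it limits the point to the supplied text.
2. **Comparison is in the plan and comes first.** Comparing a measurement with a reference method can naturally include their difference, and a side-by-side listing of ten patients would show a large bias. This also stands. A reader might infer that the plan relies on correlation alone, or that bias could not be seen. The wording does not support that. It supports only that no measure of bias is named while correlation is.
3. **Both scans may simply be reported.** A reader might infer that the better-agreeing scan could be picked after the data are seen. Nothing in the synopsis suggests selection. Both scans are planned for evaluating efficacy, and the pre-treatment MRI is a further plausible source for tumour size. What remains is a missing detail, easily stated.
4. **The magnitudes are assumed.** The noise levels and biases are not from the documents, and nothing there shows that bias of this size is likely. That is correct. The invariance in step 1 needs no such input, but the 0.99 does depend on the low noise chosen.

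A reader might also argue that correlation breaks down for percentage necrosis, because it is undefined if all ten histology values are 100%. How often that happens depends wholly on an assumed complete-ablation rate (for example 0.8^10 = 0.11 if 80% are complete), and the synopsis gives none. It is not part of the case here.

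**Conclusion.** The point holds in a limited form. For a primary endpoint of accuracy against a reference method, the only statistic the synopsis names for the quantitative analysis does not measure accuracy. A paired difference or ratio with a confidence interval does, from the same ten pairs. That conclusion rests on algebra and on the synopsis wording. The illustrated sizes (r of 0.99 at 10% noise or 0.97 at 20% noise, whether or not MRI over-reads volume by up to 50%) rest on assumed noise, bias and tumour-size distribution.

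The severity is minor. A descriptive analysis of ten patients is reasonable for proof of concept, and nothing here calls for a hypothesis test or a larger sample. The text does not show that the primary result would be misreported, nor that the full plan lacks these details.

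**What to change.** In the quantitative part of the primary outcome in the statistical analysis entry:

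- Define the comparison as the paired MRI-minus-histopathology difference, or the MRI/histopathology ratio for volumes. Make its mean with a 95% CI the main result.
- List the ten pairs.
- Report the result separately for each of the two post-treatment DCE-MRI scans, and state whether tumour size/volume is taken from the baseline MRI.
- Name any correlation coefficient and keep it supplementary.

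Limits of agreement and a pre-set tolerance for percentage necrosis are optional. At n = 10 each limit has a 95% CI half-width of about 1.24 to 1.27 SD, so the limits add little to the listed pairs.

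The cost is a wording change and a few more estimates from data already planned, doubled where both scans are reported. The estimates will look imprecise, with a half-width of about 0.72 SD for a mean difference. If a fuller plan already states the measure and the scans, confirming that and aligning the synopsis is enough.

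### Must the primary comparison name one of the two post-treatment DCE-MRI scans and state that MRI is read before pathology?

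*Combined protocol and SAP*

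**What the plan says.** All the available text is the synopsis of the combined protocol and SAP.

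- **Outcome(s).** The primary endpoint is "accuracy of MRI as method for assessment of qualitative and quantitative treatment success compared to the results of the histopathological analysis performed as reference method". MRI is the index test and pathology the reference. No scan time is given.
- **Study Product / Intervention.** "Two follow-up DCE-MRI scans will be performed for evaluation of treatment efficacy". The first is taken immediately after MR-HIFU, with the patient still sedated. The second is an outpatient scan 8 ± 2 days after treatment, that is, on days 6 to 10.
- **Schedule of procedures.** A DCE-MRI appears under the treatment visit and another under end of study. Surgery, with pathology of the specimen, is listed after both.
- **Statistical considerations, primary outcome.** The quantitative part is "Comparison and correlation of results from histopathology and DCE-MRI regarding Size/Volume of tumor and volume/percentage of tumor necrosis". The qualitative part compares pathology and DCE-MRI "regarding spatial congruence of ablated tumor tissue and width of margin". Neither part names a scan, ranks the two, or states who reads the images and when.
- **Number of participants and analysis type.** Ten patients, proof of concept, mainly descriptive statistics. No alpha, power, precision target or success threshold is stated.

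**The concern.** An accuracy study compares a defined index test with a reference. Here there are two candidate index tests, about a week apart, and the primary analysis uses a term that covers both. If the scan were chosen after pathology was known, and only the one that agreed better were reported, the apparent accuracy would be biased upwards.

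The second worry concerns reading. Congruence of the ablated area and width of the margin call for judgement, and a reader who knows the pathology could be drawn towards it. The synopsis fixes the order in which images are acquired and tissue is removed. It does not fix when the images are read, or with what knowledge. At stake is the credibility of the primary result.

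**Working it through.** The plan has no figure to reproduce: the sample of 10 is stated without a calculation. The check is therefore a reading of the text, followed by an illustration of size.

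**1. Which scan?** The sentence on the two scans gives them one shared purpose, evaluating efficacy. Efficacy is the secondary objective, so one could say this sentence does not bear on the primary comparison. But the primary objective is whether MRI can judge treatment success, so MRI's assessment of efficacy is the thing being tested. Read together, the two statements point to both scans being compared with pathology. The synopsis does not say so outright, but nothing in it suggests that one scan will be picked.

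**2. Read order.** Both scans are listed before surgery, so the images exist before the reference result does. The text is silent on blinding and on locking the reads. That is an unmentioned safeguard in a synopsis, not a rule allowing unblinded reading.

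**3. Size, if only the better scan were reported.** All inputs except n = 10 are assumed. Let histology h be standard normal and scan k = r·h + √(1 − r²)·e_k, with the two errors e correlated at c. The bias is E[max(r₁, r₂)] − E[r₁], from 200,000 simulated trials per setting:

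| True r | c = 0 | c = 0.5 | c = 0.8 | c = 0.95 |
|---|---|---|---|---|
| 0.7 | 0.092 | 0.069 | 0.045 | 0.023 |
| 0.8 | 0.062 | 0.048 | 0.032 | 0.017 |
| 0.9 | 0.032 | 0.026 | 0.017 | 0.009 |

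**4. Cross-check.** A separate simulation (40,000 trials per setting) fixed the total correlation between the scans. At true r = 0.7 and between-scan correlation 0.5, the mean r is 0.678 for a fixed scan and 0.769 for the better of two, a difference of 0.091. This setting corresponds to c = (0.5 − 0.49)/(1 − 0.49) = 0.02, and it agrees with 0.092 in the table. Over that simulation's whole range (true r 0.5 to 0.8, between-scan correlation 0.3 to 0.9) the bias runs from 0.819 − 0.782 = 0.037 to 0.611 − 0.478 = 0.133. The upper end comes from the weaker true correlation of 0.5.

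**5. Unequal scans.** Steps 3 and 4 assume that the scans are equally accurate. With assumed true correlations of 0.5/0.8, 0.6/0.9 or 0.7/0.9 and c from 0 to 0.8, taking the better of two exceeds the better scan's own mean r by only 0.000 to 0.014.

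**6. Against sampling error.** For an observed r = 0.8 and n = 10, Fisher's interval is tanh(atanh 0.8 ± 1.96/√7) = tanh(1.099 ± 0.741) = 0.343 to 0.951, a width of 0.608. At true r = 0.8 the bias in step 3 is 0.017 to 0.062, which is 3% to 10% of that width.

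**7. Binary agreement.** The same exercise on percentage agreement gives about 2 to 8 points. Little weight belongs on it, because the primary outcome defines no yes/no criterion. The only such definition, complete necrosis with a margin above 1 mm, belongs to the secondary outcome.

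**The case for a change.** The best case for a change is that even a descriptive accuracy estimate needs a defined index test. Selection bias does not average out, and it adds to an estimate that is already imprecise. The two scans need not agree, and the synopsis does not say which carries the conclusion if they differ. With a true correlation of 0.7, the chance of seeing 0.8 or more is about 30% for a fixed scan and 40% to 50% for the better of two, which is not trivial. Naming a scan and completing the MRI reads before pathology is released would cost only some wording and a signed form.

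Part of this stands. The text is silent on both matters, the two judgement-based reads are the most exposed, and a sentence of clarification would do no harm.

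The rest does not carry. The 40% to 50% arises only if one scan is suppressed, and the available text sets no threshold at 0.8 or anywhere else. If the scans disagree, showing both is the informative result for a study of 10 patients, and no ranking is needed for that. The argument for putting the second scan first, that it lies closer to the resected specimen, rests on visit order alone: the synopsis gives no surgery date or interval. Finally, the silence on reading is silence in a synopsis. It lists only key eligibility criteria, and it mentions predefined safety parameters that it does not set out. Reader procedures may well be described in a fuller plan.

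**Conclusion.** No change to the plan is called for. This is a gap that analysts fill sensibly: compare each scan with histopathology, report the two separately on every listed measure, and read the images before the pathology result reaches the reader. Nothing in the schedule stands in the way, since both scans are listed before surgery. No stated rule gives a wrong answer.

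Reported in that way, the selection bias is zero. If the better scan alone were shown, the inflation would be about 0.01 to 0.09 in r for equally accurate scans with true correlations of 0.7 to 0.9. It would reach 0.13 at a true correlation of 0.5, and nearly vanish if one scan is clearly better. These figures rest on assumed correlations and normal data, not on values in the documents. The effect of reading MRI with pathology known is not quantified and cannot be from this text. The conclusion would differ if a fuller plan said that one scan is chosen after pathology, or that MRI is read with the pathology to hand; the available text says neither.
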